5.4.1.3. Overdose

Any dose of study drug administered in excess of that specified in this protocol is considered to be an overdose. Signs and symptoms of an overdose that meet any SAE criterion must be reported as a SAE in the appropriate time frame and documented as clinical sequelae to an overdose.

There is no specific experience in the management of ibrutinib overdose in subjects. No maximum tolerated dose (MTD) was reached in the Phase 1 study in which subjects received up to 12.5 mg/kg/day (1400 mg/day). Healthy subjects were exposed up to single dose of 1680 mg. One healthy subject experienced reversible Grade 4 hepatic enzyme increases (AST and ALT) after a dose of 1680 mg. Subjects who ingested more than the recommended dosage should be closely monitored and given appropriate supportive treatment.

Refer to [Section 11.4](#) for further information regarding AE reporting.

5.4.1.4. Dose Modification for Adverse Reactions

The dose of study drug must be modified according to the dose modification guidance in [Table 2](#) and [Table 3](#) if any of the following toxicities occur:

- Grade 3 or greater neutropenia with infection or fever
- Grade 4 neutropenia (ANC <500/ μ L) for more than 7 days. See [Section 6.1](#) for instructions regarding the use of growth factor support.
- Grade 3 thrombocytopenia (platelets <50,000/ μ L) in the presence of clinically significant bleeding events.
- Grade 4 thrombocytopenia (platelets <25,000/ μ L).

- Grade 3 or greater non-hematological toxicity (Note: [Table 3](#) includes recommendations for cardiac failure and cardiac arrhythmias)
- Grade 2 cardiac failure ([Table 3](#))
- Any other Grade 4 or unmanageable Grade 3 hematological toxicity.

If clinically indicated, the use of anticoagulants or antiplatelet agents may be considered for the thromboprophylaxis of atrial fibrillation ([Section 6.2.4](#)).

In the event that the investigator feels deviation from the recommendations above is required, please consult the Medical Monitor.

Dose changes must be recorded in the Dose Administration eCRF. Study treatment should be discontinued in the event of an ibrutinib-related toxicity requiring dose hold lasting more than 28 days, unless reviewed and acknowledged by the Medical Monitor.

Note: Temporary withholding of single-agent ibrutinib for as little as 7 days can cause a transient worsening of disease and/or of constitutional symptoms. Study drug should be re-started as soon as clinically appropriate.

Table 2. Ibrutinib/ Placebo Dose Modifications for Events not Specified in Table 3

Occurrence	Action to be Taken
First	Withhold study drug until recovery to Grade ≤ 1 or baseline; may restart at original dose level ^a
Second	Withhold study drug until recovery to Grade ≤ 1 or baseline; may restart at 1 dose level lower (ie, 280 mg/day for 420 mg/day dose)
Third	Withhold study drug until recovery to Grade ≤ 1 or baseline; may restart at 1 dose level lower (ie, 140 mg/day for 420 mg/day dose)
Fourth	Discontinue study drug

a. When resuming treatment, restart at the same or lower dose based on benefit-risk evaluation. If the toxicity reoccurs, reduce daily dose by 140 mg.

For required dose modification for hepatic impairment refer to [Section 5.4.1.6](#) and for concomitant treatment with CYP3A inhibitors refer to [Section 6.2.1.1](#).

Table 3. Ibrutinib/Placebo Dose Modifications for Cardiac Failure or Cardiac Arrhythmias

Events	Occurrence	Action
Grade 2 cardiac failure	First	Hold study drug until recovery to Grade ≤ 1 or baseline; restart at 1 dose level lower (2 capsules [ie, 280 mg daily])
	Second	Hold study drug until recovery to Grade ≤ 1 or baseline; restart at 1 dose level lower (1 capsules [ie, 140 mg daily])
	Third	Discontinue study drug
Grade 3 cardiac arrhythmias	First	Hold study drug until recovery to Grade ≤ 1 or baseline; restart at 1 dose level lower (2 capsules [ie, 280 mg daily]) ^a
	Second	Discontinue study drug
Grade 3 or 4 cardiac failure Grade 4 cardiac arrhythmias	First	Discontinue study drug

a. Evaluate the benefit-risk before resuming treatment.

5.4.1.5. Leukocytosis/Leukostasis

A high number of circulating malignant cells (>400,000/ μ L) may confer increased risk of leukostasis; these subjects should be closely monitored. Administer supportive care such as hydration and/or leukopheresis as indicated. Ibrutinib may be temporarily held, and Medical Monitor should be contacted.

5.4.1.6. Dose Modification for Hepatic-Impaired Subjects

Ibrutinib is metabolized in the liver and therefore subjects with clinically significant hepatic impairment at the time of screening (Child-Pugh Class B or C) are excluded from study participation. For subjects who develop mild liver impairment while on study (Child-Pugh Class A), the recommended dose reduction for ibrutinib/placebo is to a level of 280 mg daily (two capsules). For subjects who develop moderate liver impairment while on study (Child-Pugh Class B), the recommended dose reduction is to a level of 140 mg daily (one capsule). Subjects who develop severe hepatic impairment (Child-Pugh Class C) must hold study drug until resolved to moderate impairment (Child-Pugh Class B) or better. Monitor subjects for signs of toxicity and follow dose modification guidance as needed (Refer to [Appendix K](#)).

5.4.2. Venetoclax (ABT-199)

5.4.2.1. Formulation/Packaging/Storage

Venetoclax tablets are provided as film coated tablets containing 10 mg, 50 mg, or 100 mg of venetoclax.

The venetoclax tablets will be packaged in blister packs during initial dose ramp up period and in high density polyethylene (HDPE) plastic bottles thereafter to accommodate the study design.

Each container will be labeled as required per country requirements. Labels must remain affixed to the container.

The venetoclax supplied in this study is for investigational use only, and must only be used within this study. All study drug must be maintained under adequate security and stored under conditions specified on the label until dispensed for subject use or returned to Pharmacyclics or representative.

The tablets must be stored at a controlled room temperature of 15° to 25°C (59° to 77°F).

5.4.2.2. Prophylaxis and Management of Tumor Lysis Syndrome

Venetoclax can cause rapid reduction in tumor and thus poses a risk for TLS in the initial 5-week ramp-up phase. Changes in electrolytes consistent with TLS that require prompt management can occur as early as 6-8 hours following the first dose of venetoclax and at each dose increase. The risk of TLS is a continuum based on multiple factors, including tumor burden and comorbidities. Subjects with high tumor burden are a greater risk of TLS when initiating venetoclax. Reduced renal function further increases the risk. The risk may decrease as tumor burden decreases with venetoclax treatment.

Subjects at high risk of TLS (at least one lesion ≥ 10 cm; or at least one lesion ≥ 5 cm plus circulating lymphocytes $>25,000$ cells/ μ L) will be hospitalized during the first 24-48 hours of treatment for TLS monitoring and hydration. Hospitalization should be considered for subjects with medium risk of TLS and baseline creatinine clearance <80 mL/min. Hospitalization for subjects lacking immediate access to a facility capable of correcting TLS promptly or for subjects who are otherwise considered at risk for TLS is allowed at the discretion of the investigator.

In all subjects, perform tumor burden assessments, including radiographic evaluation (eg, CT scan), assess blood chemistry (potassium, uric acid, phosphorus, calcium, and creatinine) and correct pre-existing abnormalities prior to initiation of treatment with venetoclax in Cycle 4.

In all subjects, assess patient-specific factors for level of risk of TLS and provide prophylactic hydration and anti-hyperuricemics to subjects prior to first dose of venetoclax to reduce risk of TLS. Employ more intensive measures (intravenous hydration, frequent monitoring, and hospitalization) as overall risk increases.

Table 4. TLS Prophylaxis Based on Tumor Burden from Clinical Trial Data (consider all co-morbidities before final determination of prophylaxis and monitoring schedule)

Tumor Burden		Prophylaxis		Blood Chemistry Monitoring ^{c,d}
		Hydration ^a	Anti-hyperuricemics	Setting and Frequency of Assessments
Low	All LN <5 cm AND ALC <25 x10 ⁹ /L	Oral (1.5-2 L)	Allopurinol ^b	Outpatient 
 Pre-dose, 6 to 8 hours, 24 hours at first dose of 20 mg and 50 mg Pre-dose at subsequent ramp-up doses
Medium	Any LN 5 cm to <10 cm OR ALC ≥25 x10 ⁹ /L	Oral (1.5-2 L) and consider additional intravenous	Allopurinol ^b	Outpatient 
 Pre-dose, 6 to 8 hours, 24 hours at first dose of 20 mg and 50 mg Pre-dose at subsequent ramp-up doses Consider hospitalization for subjects with CrCl <80mL/min at first dose of 20 mg and 50 mg; see below for monitoring in hospital
High	Any LN ≥10 cm OR ALC ≥25 x10 ⁹ /L AND any LN ≥5 cm	Oral (1.5-2 L) and intravenous (150-200 mL/hr as tolerated)	Allopurinol ^b ; consider rasburicase if baseline uric acid is elevated	In hospital at first dose of 20 mg and 50 mg 
 Pre-dose, 4, 8, 12 and 24 hours Outpatient at subsequent ramp-up doses 
 Pre-dose, 6 to 8, and 24 hours

ALC = absolute lymphocyte count; LN = lymph node

- Administer intravenous hydration for any patient who cannot tolerate oral hydration.
- Start allopurinol or xanthine oxidase inhibitor 2 to 3 days prior to initiation of venetoclax.
- Evaluate blood chemistries (potassium, uric acid, phosphorus, calcium, and creatinine); review in real time.
- For subjects at risk of TLS, monitor blood chemistries at 6 to 8 hours and at 24 hours at each subsequent ramp-up dose. A ±30-minute window is acceptable for the 4 and 8 hr chemistry assessments, a ±1 hr window is acceptable for the 12-hour chemistry assessments, and a ±2-hour window is acceptable for the 24-hour chemistry assessments.
- Hematology and Serum Chemistry may be collected up to 24 hours prior to each venetoclax ramp-up (Cycle 4 Weeks 2-4 and Cycle 5 Week 1), to allow for flexibility in start of ramp-up dose. Hematology and serum chemistry can be drawn on day of dosing to allow for comparisons, but results are not required before dosing decision is made

Hydration: Ensure adequate hydration prior to initiating therapy with venetoclax and throughout the ramp-up phase, especially the first day of each ramp-up dose. Administer intravenous (IV) fluids as indicated based on overall risk of TLS or for those who cannot maintain adequate oral hydration.

Anti-hyperuricemic agents: Administer uric acid reducing agents (eg, allopurinol).

Start 2-3 days prior to initiation of venetoclax; consider continuing through the ramp-up phase.

Laboratory Assessments:

Pre-dose: Assess blood chemistries (specifically creatinine, uric acid, potassium, phosphorus, and calcium) prior to initiating venetoclax to evaluate kidney function and correct pre-existing hyperuricemia, hyperkalemia, hyperphosphatemia, or hypocalcemia to normal levels before

administering venetoclax. Reassess blood chemistries before starting each subsequent ramp-up dose of venetoclax.

Post-dose: For subjects at low or medium risk of TLS, monitor blood chemistries at 6-8 hours and at 24 hours after initiating venetoclax at the 20 mg and 50 mg doses. For subjects at high risk of TLS, monitor blood chemistries in the hospital at 4, 8, 12, and 24 hours after initiating venetoclax at the 20 mg and 50 mg doses; subsequent ramp-up doses can be administered in the outpatient setting with monitoring of blood chemistries at 6-8 hours and at 24 hours after initiating venetoclax. Electrolyte abnormalities should be corrected promptly. The next dose of venetoclax should not be administered until the 24-hour blood chemistry results have been evaluated and hyperuricemia, hyperkalemia, hyperphosphatemia, or hypocalcemia are corrected to normal levels.

Hospitalization: Based on investigator assessment of TLS risk, subjects at high risk of TLS require hospitalization on the day of the first dose of venetoclax 20 mg and 50 mg doses for more intensive prophylaxis and monitoring through the first 24 hours. Subsequent ramp-up doses can be administered on an outpatient basis; however, hospitalization may be considered based on reassessment of risk. See [Appendix H](#) for TLS Risk Categories and [Appendix J](#) for Recommendations for Initial Management of Electrolyte Abnormalities and Prevention of Tumor Lysis.

5.4.2.3. Dose and Administration

Venetoclax tablets are taken orally once daily with a meal and water. Venetoclax tablets should be swallowed whole and not chewed, crushed, or broken prior to swallowing. During cycles with ibrutinib combination dosing, ibrutinib and venetoclax should be taken together at the same time, with 8 ounces of water and with a meal (or within 30 minutes after the completion of a meal). For subjects not able to swallow all ibrutinib capsules and venetoclax tablets at the same time, administration should be completed within a 60-minute window. If the subject misses a dose of venetoclax within 8 hours of the time it is usually taken, the subject should take the missed dose as soon as possible on the same day and resume the normal daily dosing schedule. If a subject misses a dose by more than 8 hours, the subject should not take the missed dose and resume the usual dosing schedule the following day.

In cases of vomiting after taking venetoclax, no additional dose (tablets) should be taken that day. The next dose should be taken at the usual time the following day.

The first dose of venetoclax will be delivered in the clinic (or in the hospital depending on TLS risk category) on Cycle 4 Day 1. Seven doses of daily venetoclax must be taken at each dose level in the venetoclax dose ramp up, thus each level of the ramp up may require more than 7 days if doses are missed or held. After completion of the 5-week dose ramp up, subsequent dosing is typically on an outpatient basis. On days of PK sample collection (C2D1 and C6D1), ibrutinib and venetoclax should be administered at the same time or as close together in time as possible in the clinic. Venetoclax will be dispensed to subjects in blister packs through the dose

ramp up period, and in bottles at each subsequent visit. Unused venetoclax dispensed during previous visits must be returned to the site and drug accountability records ([Section 12.8](#)) updated at each visit. Returned tablets must not be redispensed to anyone.

Assess subject-specific factors for level of risk of TLS and provide prophylactic hydration and anti-hyperuricemics to subjects prior to first dose of venetoclax to reduce risk of TLS. Venetoclax will be administered orally once daily (QD) beginning with a dose ramp-up period. As shown in [Figure 1](#), the initial venetoclax dose is 20 mg QD. After one week of treatment at 20 mg QD, the dose will be escalated to 50 mg QD followed by subsequent increases, each after one week, to 100 mg QD, 200 mg QD and the maximum dose of 400 mg QD. The 5-week ramp-up dosing schedule is designed to gradually reduce tumor burden (debulk) and decrease the risk of TLS. All study subjects will be categorized in Cycle 3 according to their risk for developing TLS. Their dose management including during the dose ramp-up period will be conducted in accordance with their risk for developing TLS (see [Section 5.4.2.5](#)) and may include dose delay and/or dose reduction as required for prophylaxis and management of TLS.

5.4.2.4. Overdose

There is no specific antidote for venetoclax. For subjects who experience overdose, closely monitor and provide appropriate supportive treatment; during ramp-up phase interrupt venetoclax and monitor carefully for signs and symptoms of TLS along with other toxicities (see [Section 1.3.3](#) and [Section 5.4.2](#)). Based on venetoclax large volume of distribution and extensive protein binding, dialysis is unlikely to result in significant removal of venetoclax.

5.4.2.5. Dose Modification for Adverse Reactions

Dosing interruption and/or dose reduction may be required. See [Table 5](#) for dose modifications for hematologic and other toxicities related to venetoclax. For subjects who have had a dosing interruption greater than 1 week during the first 5 weeks of ramp-up phase or greater than 2 weeks when at the daily dose of 400 mg, reassess for risk of TLS to determine if reinitiation with a reduced dose is necessary (eg, all or some levels of the dose ramp-up schedule).

Table 5. Venetoclax Recommended Dose Modifications for Toxicities^a

Event	Occurrence	Action
Tumor Lysis Syndrome		
Blood chemistry changes or symptoms suggestive of TLS (see Howard Criteria in Appendix I)	Any	Withhold the next day's dose. If resolved within 24-48 hours of last dose, resume at the same dose.
		For any blood chemistry changes requiring more than 48 hours to resolve, resume at a reduced dose (see Table 6).
		For any events of clinical TLS ^b , resume at a reduced dose following resolution (see Table 6).
Non-Hematologic Toxicities		
Grade 3 or 4 non-hematologic toxicities	1 st occurrence	Interrupt venetoclax Once the toxicity has resolved to Grade 1 or baseline level, venetoclax therapy may be resumed at the same dose. No dose modification is required.
	2 nd and subsequent occurrences	Interrupt venetoclax. Follow dose reduction guidelines in Table 6 when resuming treatment with venetoclax after resolution. A larger dose reduction may occur at the discretion of the investigator
Hematologic Toxicities		
ANC <1000/ μ L with infection or fever; or CTCAE Grade 4 hematologic toxicities (ANC <500/ μ L, WBC <1000/ μ L, platelets <25,000/ μ L, life threatening anemia)	1 st occurrence	Interrupt venetoclax. To reduce the infection risks associated with neutropenia, granulocyte-colony stimulating factor (G-CSF) may be administered with venetoclax if clinically indicated. Once the toxicity has resolved to ANC >1500/ μ L or baseline level, venetoclax therapy may be resumed at the same dose.
	2 nd and subsequent occurrence	Interrupt venetoclax. Consider using G-CSF as clinically indicated. Follow dose reduction guidelines in Table 6 when resuming treatment with venetoclax after resolution. Additional dose reductions may occur at the discretion of the physician.

Consider discontinuing venetoclax for subjects who require dose reductions to less than 100 mg for more than 2 weeks.

- a. Adverse reactions were graded using NCI CTCAE version 4.03.
b. Clinical TLS was defined as laboratory TLS with clinical consequences such as acute renal failure, cardiac arrhythmias, or sudden death and/or seizures.

Table 6. Dose Modification for Toxicity during Venetoclax Treatment

Dose at Interruption, mg	Restart Dose, mg ^a
400	300
300	200
200	100
100	50
50	20
20	10

- a. During the ramp-up phase, continue the reduced dose for 1 week before increasing the dose.

For required dose modification for concomitant treatment with CYP3A inhibitors refer to [Section 6.2.1.2](#).

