5.4.2.6. Management of Neutropenia

Nonclinical and clinical experience indicates that venetoclax may cause neutropenia. Subjects with a history of neutropenia who have received multiple prior therapies and/or have significant bone marrow involvement may be at a particularly high risk.

CTCAE Grade 3 or 4 neutropenia has been reported in patients treated with venetoclax. Complete blood counts should be monitored throughout the treatment period. Dose interruptions or dose reductions are recommended for subjects with severe neutropenia. Supportive measures including antimicrobials for any signs of infection and prophylactic use of growth factors (eg, G-CSF) should be considered.

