5.4.2.7. Management of Hematologic Toxicities Other Than Neutropenia or Lymphopenia

Venetoclax treatment should be withheld for any CTCAE Grade 4 hematologic toxicity. Once the toxicity has resolved to Grade 1 or baseline level (recovery), venetoclax may be re-started at the same dose. If the toxicity recurs, the dose reduction guidelines in [Table 5](#) should be followed when resuming study treatment following resolution. Additional dose reductions may occur at the discretion of the physician.

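### Venetoclax Table 5 gives a neutrophil-based restart test for Grade 4 platelet and hemoglobin events, at odds with Section 5.4.2.7; the cell should be aligned

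*Protocol*

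**What the plan says.** Section 5.4.2.5 directs sites to Table 5 for venetoclax dose changes for hematologic and other toxicities. The hematologic row has five triggers: ANC below 1000/µL with infection or fever, ANC below 500/µL, WBC below 1000/µL, platelets below 25,000/µL, and life-threatening anemia. At first occurrence the restart condition opens "Once the toxicity has resolved to ANC" and is completed by a value above 1500/µL or baseline level; venetoclax may then resume at the same dose. No other restart value is given in that cell.

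Section 5.4.2.7 is headed "Management of Hematologic Toxicities Other Than Neutropenia or Lymphopenia". Its trigger matches the Grade 4 part of the Table 5 row: "Venetoclax treatment should be withheld for any CTCAE Grade 4 hematologic toxicity". Its restart rule is different: "Once the toxicity has resolved to Grade 1 or baseline level (recovery), venetoclax may be re-started at the same dose". It then refers to Table 5 only for a toxicity that recurs.

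Three nearby provisions help:
- The non-hematologic row of Table 5 says "Once the toxicity has resolved to Grade 1 or baseline level, venetoclax therapy may be resumed at the same dose", which agrees with its own section, 5.4.2.8.
- Section 5.4.2.6, on neutropenia, gives no restart value. It says only "Dose interruptions or dose reductions are recommended for subjects with severe neutropenia".
- For ibrutinib, Section 5.4.1.4 has the same platelet trigger (below 25,000/µL), and Table 2 restarts at Grade 1 or better, or baseline.

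**The concern.** A neutrophil count says nothing about whether platelets or hemoglobin have recovered. A site working from Table 5 alone has two ways to apply the cell to a first Grade 4 platelet or hemoglobin event, and neither gives the rule in 5.4.2.7. Taken literally, an adequate ANC is enough and the affected count is never checked. If the ANC part is set aside as inapplicable, only return to baseline is left, and the Grade 1 alternative is lost.

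The second way can lengthen a hold. For an interruption of more than 1 week in ramp-up, or one "greater than 2 weeks when at the daily dose of 400 mg, reassess for risk of TLS", Section 5.4.2.5 asks the site to decide whether to restart at a reduced dose, for example by repeating some or all ramp-up steps. It can also separate the two drugs: after one platelet event, ibrutinib could resume at Grade 1 while venetoclax stays on hold.

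The rule also matters when venetoclax is reintroduced, since nothing confines Section 5.4.2.5 to the first course. Appendix D allows up to 24 cycles in the MRD cohort and Appendix E up to 12 in the Fixed Duration cohort.

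**Working it through.** The plan states no figure to reproduce. The check compares decision rules for a first Grade 4 platelet or hemoglobin event.

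**Where the odd value sits.** Of the five triggers in the Table 5 row, two are ANC values and three are not (WBC, platelets, anemia). Four places give a first-occurrence restart test for graded venetoclax toxicity: the two Table 5 rows, 5.4.2.7 and 5.4.2.8. Three of the four use Grade 1 or baseline; only the hematologic cell differs.

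**The readings side by side.**

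| Reading of the cell | Restart test for a platelet event | Against 5.4.2.7 |
|---|---|---|
| A. ANC alone is enough | ANC above 1500/µL, whatever the platelet count | Looser |
| B. ANC part cannot apply | Platelets back to baseline | Stricter, or equal |
| C. ANC part for neutropenia; 5.4.2.7 for the rest | Grade 1 or baseline | Same |

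Example for A: with platelets still at 20,000/µL and ANC at 2,000/µL, the literal cell is met and 5.4.2.7 is not.

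**Size under reading B.** Let b be the baseline platelet count and g the lowest Grade 1 count.
- 5.4.2.7 allows restart once the count reaches min(b, g).
- Table 5, read as baseline only, allows it once the count reaches b.
- Gap = b − min(b, g). This is positive only if b > g.

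**Where the gap must be zero.** Inclusion criterion 4 admits platelets above 30,000/µL. Section 5.4.1.4 prints the Grade 3 limit as "Grade 3 thrombocytopenia (platelets <50,000" per µL. Grade 1 is milder than Grade 3, so g is at least 50,000/µL.
- b = 30,001: min(b, g) = 30,001, gap 0.
- b = 49,999: min(b, g) = 49,999, gap 0.

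The two rules therefore agree for baselines from 30,001 to 49,999/µL.

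**An illustration of a positive gap.** Table 5 is graded by CTCAE v4.03, whose Grade 1 platelet cut-off is not printed in the documents. The only printed Grade 1 platelet scale is the IWCLL one in Appendix L, a fall of 11% to 24% from the pre-treatment value, so this example is indicative only. It assumes that the counts are below the laboratory's normal limit.
- Baseline 120,000/µL: the Grade 1 band runs from 120,000 × 0.76 = 91,200 to 120,000 × 0.89 = 106,800/µL.
- Gap = 120,000 − 91,200 = 28,800/µL.
- At 100,000/µL the fall is 20,000 / 120,000 = 16.7%. 5.4.2.7 allows restart; reading B does not.

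**Which rule was intended.** The heading of 5.4.2.7 makes it the specific section for these cytopenias. It gives its own first-event rule and uses Table 5 only on recurrence. Ibrutinib Table 2 has the same recovery standard. All three support reading C. Against this, 5.4.2.5 sends hematologic toxicities to Table 5 without qualification, the first-occurrence cell has no pointer to 5.4.2.7, and no sentence says which text governs.

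**The case against.** The strongest reply is that the two texts can be reconciled. Section 5.4.2.7 is the specific rule, Table 5 is a general summary of recommended modifications, and both share the baseline limb. A clinician who reads both would use the ANC value for neutropenia and Grade 1 or baseline for the rest. Both texts are also permissive: restarting at Grade 1 follows 5.4.2.7, and waiting for baseline breaches neither. A long hold calls for a TLS reassessment, not automatic repetition of the ramp-up.

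Most of this stands, and it limits the point. A reader might infer that the two provisions contradict each other on every reading. They do not; reading C reconciles them and is probably what was meant. A reader might also infer that Table 5 lets venetoclax restart while platelets are still at Grade 4. The cell requires the toxicity itself to have resolved, so that is an unlikely use of it, and a concurrent ibrutinib hold for the same platelet value gives sites a second benchmark.

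What the reply does not remove is that reading C has to be assembled from a heading, a recurrence clause and the partner drug's table. Section 5.4.2.5 sends the site to a cell that states a neutrophil value as the recovery test.

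**Conclusion.** The point holds as a minor dosing-safety correction. The cell is wrong as worded for platelets and hemoglobin, because it conflicts with the protocol's own specific section when read alone and nothing states precedence. Grade 1 or baseline is the likely intended rule; that is an inference from the three indications above, not something the protocol says.

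If the cell is taken as baseline only, the rules differ only for subjects whose baseline is better than the lowest Grade 1 value, and they agree for baseline platelets of 30,001 to 49,999/µL. The documents give neither the CTCAE Grade 1 cut-offs for platelets and hemoglobin nor the frequency of such holds, so no number of affected subjects can be given.

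There is no conflict for neutropenia: 5.4.2.6 has no restart value, and the ANC test belongs there. A reader might also infer that WBC events have no rule at all. The heading of 5.4.2.7 excludes only neutropenia and lymphopenia, and its trigger covers any Grade 4 hematologic toxicity, so what is missing for WBC is detail. Nor does the point reach the results: no endpoint, sample size or test depends on this cell.

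**What to change.** In the first-occurrence hematologic cell of Table 5, limit the test of ANC above 1500/µL or baseline to neutropenia. For the other Grade 4 hematologic toxicities in the row, write Grade 1 or baseline level and add a pointer to 5.4.2.7. Sections 5.4.2.6 to 5.4.2.8 need no change.

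The cost is the wording of one cell. In practice, some platelet or hemoglobin holds may become longer at sites that took the ANC test literally, and some shorter at sites that waited for full return to baseline.
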